# SINGLE vs MULTI-ORIFICE CATHETER STUDY FORM

ANESTHESIOLOGIST CODE \_\_\_ Date \_\_\_ Time \_\_\_ room \_\_\_

Anesthesiologist : Attending Fellow CA-3 CA-2 CA-1

Patient Description Age: \_\_\_ Gest Age: \_\_\_ Ht/Wt: \_\_\_ G \_\_\_ P \_\_\_

Cervical dilation \_\_\_ cm Estimated Level of placement: L \_ - L \_

Relevant patient's comorbidities: \_\_\_\_\_

EPIDURAL KIT: ARROW BBRAUN

Time: loss of resistance to Epidural needle removed following successful placement \_\_\_ minutes : \_\_\_ seconds

Loss of Resistance Unable to get Loss Equivocal Loss Clear Loss

Dural Puncture epidural used ? YES NO

If Dural Puncture Epidural used, CSF in the spinal needle? YES NO

Dural Puncture Epidural used because of:  Equivocal loss  As part of technique

Because catheter wouldn't thread and wanted to make sure I was midline

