## **OBJECTIVES**

The aim of the study is to assess if there is a difference in ability to thread the epidural catheter (measured in time to thread) from two different pain management kits: Arrow® and B.Braun®. In order to improve patient care at U of M, if there is a difference in the time to thread epidurals with one kit over the other (i.e. one epidural catheter threads more easily than the other), we would like to use the kit with decreased time to thread in the future. We would like to make this comparison based on data.

Our hypothesis is that there is no difference in the average time required for clinicians to thread the epidural catheters from the Arrow® and B.Braun® pain management kits.

The primary outcome is to compare the number of epidural threading attempts between the Arrow® and B.Braun® pain management kits.

Secondary objectives of this study are to compare the difference in average time required to advance the epidural catheter, the number of epidural needle manipulations once the epidural space has been established, the incidence of unintended dural punctures, the incidence of paresthesia, and the incidence of epidural intravascular cannulations between the two different kit vendors.

Our findings may not be generalizable to other facilities due to local practices (presence or absence of trainees, training level of the residents, obesity of patients, etc.) but data will be made publically available. This project is primarily intended to improve patient care at U of M via scientific level analysis.

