### *Statistical Analysis*

Statistical analysis will be performed using SAS 9.3 (SAS Institute, Cary, NC). The

primary outcome will be the success rate of epidural catheter threaded with each epidural kit, which will be compared by group using a chi-square test or Fisher's exact test, as appropriate. The secondary outcomes will be analyzed as follows: the difference in number of epidural attempts will be compared using the Mann-Whitney test; the difference in time to perform the epidural start to finish defined as the time the epidural needle is inserted through the patient's skin to the end of the catheter thread will be compared using the Student's t-test; the difference in the incidence of epidural needle manipulations once the epidural space has been established will be compared using the Chi-Square or Fisher's exact test, as appropriate; the difference in incidence of unintended dural puncture, paresthesia, and intravascular cannulations will be compared using the chi-square or Fisher's exact test, as appropriate. In addition, the difference in unsatisfactory labor analgesia with Arrow® and B.Braun® kits will be compared through the chi-square or Fisher's exact test, as appropriate, by looking at the difference in percentages of patients who have a verbal analogue pain score equal or less than 10 (scale 0 to 100) at 30 minutes following epidural medication administration. A p-value of 0.05 throughout will be considered statistically significant.

All statistical analyses will be performed using SAS 9.3 (SAS Institute, Cary, NC).

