### *Minimizing the Risk for Subjects*

This project is a comparison of standardized epidural technique between two different epidural catheter kits that are currently in use in major academic institutions in the country and at the University of Michigan. There is no hypothesized difference in the ability to thread the

epidural catheter between the two kits. The research involves no risk to the patient subject beyond risk inherent to epidural placement.

Waiver of informed consent will not affect the rights, welfare, or pain management of the subject, given that in either scenario, they will receive a standard of care epidural.

No identifiable information will be collected and retained about the subjects after completion of the patient's vaginal or cesarean delivery. All data will be recorded using a numerical code to be assigned to each individual study case. The master file will be kept in a locked filing cabinet in the principal investigator's office. All data will be analyzed in a coded fashion. Attention to strict confidentiality will be maintained; no attempts will be made to identify individual study subjects.

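### Both time windows in the plan can include an optional dural puncture done before the catheter is tried, so neither isolates the time to advance the catheter (a secondary outcome; size unknown)

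*Combined protocol and SAP*

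**What the plan says.** - **Objectives.** The aim is ability to thread the catheter, "measured in time to thread". The secondary objectives begin with a plan to "compare the difference in average time required to advance the epidural catheter". The investigators would like to adopt the kit with the shorter time.
- **Study form.** There is one duration field: "Time: loss of resistance to Epidural needle removed following successful placement". No field records when the catheter was first tried.
- **Study form, dural puncture items.** One item asks about "Dural Puncture epidural used" (yes or no). Another, "Dural Puncture Epidural used because of", offers three reasons: an unclear loss of resistance, routine technique, or a catheter that would not thread. The duration of the step is not recorded.
- **Statistical Analysis.** Time runs from the needle being "inserted through the patient's skin to the end of the catheter thread will be compared using the Student's t-test". No covariate is named, and the dural puncture step is not mentioned.
- **Table 2.** Use of the step is compared by kit, but it is not linked to time or broken down by reason.
- **Technique.** The section on equipment and technique does not describe the step. The section on minimizing risk says "This project is a comparison of standardized epidural technique between two different epidural catheter kits".

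**The concern.** Two of the three listed reasons (routine technique and unclear loss of resistance) are not responses to a failed thread. A dural puncture done for either would normally come once a loss has been felt and before the catheter is inserted. Its duration then counts as time to thread on the form, and also in the wider skin-to-thread window, so choosing between the two windows does not remove it. Only the third reason belongs to threading difficulty.

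Two things follow. First, the step adds variance unrelated to the catheter, which costs power. Second, kits are allocated open label in whole weeks, about eight in all. Operators who favour the step may cluster in one kit's weeks, or operators may choose it more often with one kit. The time the step takes would then appear as a kit difference in threading time, the measure that the Objectives tie to future kit choice.

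**Working it through.** **The plan's own figure.** The only sample-size figure is 107 per group, for the binary primary outcome. With 0.11 versus 0.01, two-sided 0.05 and 80% power, the pooled formula gives (1.96·√(2·0.06·0.94) + 0.842·√(0.1079 − 0.0001))² / 0.10² ≈ 87.4. The continuity correction, (87.4/4)·(1 + √(1 + 4/(87.4·0.10)))², gives 106.4, so 107. This reproduces exactly and does not involve time. The plan states no power, SD or target difference for time.

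**Inputs for time.**
- From the documents: 120 placements per kit, about 30 per week, about 8 weeks.
- Assumed: the step adds d = 45 to 90 s; it is used in p = 10% to 50% of placements; the SD of the rest of the window is s = 60 to 120 s; and the comparison would have 80% power without the step.

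**Added variance.** Variance = s² + p(1−p)d². Power = Φ(2.80·s/√variance − 1.96).

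| s | d | p | Variance ratio | Power |
|---|---|---|---|---|
| 120 | 45 | 0.1 | 14582/14400 = 1.01 | 0.795 |
| 60 | 90 | 0.3 | 5301/3600 = 1.47 | 0.64 |
| 60 | 90 | 0.5 | 5625/3600 = 1.56 | 0.61 |

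The effect runs from negligible to a loss of about 19 points of power.

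**Shift if use differs between kits.** Shift = d × difference in use. A 20-point difference gives 45 × 0.2 = 9 s to 90 × 0.2 = 18 s. With p = 0.3 and no kit effect, SE = √(2·variance/120). The nominal 5% test then rejects with these probabilities:
- d = 45, s = 120: SE 15.7 s, 0.09
- d = 45, s = 60: SE 8.2 s, 0.20
- d = 90, s = 120: SE 16.4 s, 0.20
- d = 90, s = 60: SE 9.4 s, 0.48

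**How likely is a 20-point difference?** If use is independent between placements, the SE of the difference is √(2·0.3·0.7/120) = 5.9 points. Twenty points is then 3.4 SE (two-sided p about 0.0007), and the t-test's error already contains this variation, so its level stays at 5%.

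With use clustered by week at an assumed intraclass correlation (ICC), the design effect is 1 + 29·ICC. The unconditional rejection rate is 2·(1 − Φ(1.96/√f)), where f = (s² + 0.21·d²·design effect)/(s² + 0.21·d²).

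| ICC | Design effect | SE of difference in use (points) | P(20 points or more) | Rejection rate, d = 45, s = 120 | Rejection rate, d = 90, s = 60 |
|---|---|---|---|---|---|
| 0.01 | 1.29 | 6.7 | 0.003 | 0.05 | 0.06 |
| 0.05 | 2.45 | 9.3 | 0.03 | 0.05 | 0.11 |
| 0.10 | 3.90 | 11.7 | 0.09 | 0.06 | 0.16 |

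Systematic operator choice is a separate route to imbalance. The documents give nothing from which to size it.

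**The case against.** The strongest reply is that this is a small refinement of unknown size, and much of that stands.

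- **The error rate.** A reader might infer that the time test has a false-positive rate of up to 48%. The documents do not support that. The 9% to 48% range applies only once a 20-point imbalance is present. Independent use would almost never produce one, and chance alone does not inflate the test. Inflation needs week-level clustering, which is part of the wider problem of analysing whole-week allocation as independent placements, or systematic choice by operators.
- **The inputs.** Frequency, duration and SD are all assumed, as is the 80% baseline. The low end is no material loss.
- **The sequence.** No section says when the step is done or which loss of resistance starts the clock. The plan also allows a second loss of resistance after a failed thread, and a step done for an unclear loss at that point would follow threading difficulty.
- **Adjustment.** A reader might infer that a covariate for the step should enter the main model. That is not supported. The step is chosen after the week's kit is known, and the kits contain differently named needles. An unclear loss of resistance could therefore itself depend on the kit, and adjustment could remove part of a real kit effect.
- **Existing safeguards.** Table 2 would already show an overall imbalance in use, and the reason is recorded, so a sensitivity analysis remains possible. It is just not prespecified.
- **The conflict between windows.** The form and the Statistical Analysis section define different times, and a whole-procedure time could legitimately include the step. That conflict matters more, and a fix to the form alone would widen it.

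What survives is that neither window measures the time the Objectives name, and correcting this costs almost nothing before data collection.

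**Conclusion.** The point holds as a minor improvement to a secondary outcome. On the natural reading of the form, both time windows include an optional dural puncture done before the catheter is tried, and the planned test does not deal with it. The certain consequence, if the step is used in some but not all placements, is extra variance. Bias is possible only if use differs between kit weeks through clustering or operator choice. Under the assumed ranges, power falls from 80% to between 61% and almost 80%, and the unconditional error rate is 5% to 11% for an ICC of 0.01 to 0.05. None of these sizes can be established from the documents, and the true effect may be negligible.

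Because the Objectives frame the aim around time, a reader might infer that the trial's main conclusion is at risk. It is not. The primary outcome is stated as attempts in the Objectives and as threading success in the Statistical Analysis section. Neither is a time, and the 107 per group does not depend on this point.

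**What to change.** 1. **Preferred, before data collection.** Reword the form's time line so that the clock starts when the catheter is first inserted into the needle and stops when it has been threaded successfully and the needle removed. It should keep running through any manoeuvre or repeat loss of resistance that follows a failed thread. Amend the time definition in the Statistical Analysis section to the same window. The cost is one line on the form and one sentence in the plan.
2. **If the present window is kept.** Leave the unadjusted comparison as the main analysis. Tabulate the three dural puncture reasons by kit. Prespecify a sensitivity analysis that excludes, or adjusts for, the step done as routine technique. State beside it that the step is chosen after the kit is known and that an unclear loss of resistance may depend on the kit's needle. The cost is one table and one extra model, from data already on the form.
3. **In either case.** Reconcile the technique description and the statement that technique is standardized with the form's treatment of the step as optional. Whether the step belongs to the technique is for the investigators to state.

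No extra patients or procedures are needed.

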## Ease of Threading the Epidural Catheter

- |   |                              |
|---|------------------------------|
|  Easy thread without further maneuvers  |                              |
|  hydrodissection, then catheter:  | Thread Did not thread |
|  new catheter from the same brand, then catheter:   | Thread Did not thread |
|  Rotated the needle, then catheter:   | Thread Did not thread |
|  Changed needle angle, then catheter:   | Thread Did not thread |
|  Withdrawal and re-advanced the needle with an additional LOR (this count as an additional attempt), then catheter: | Thread Did not thread |
|  Advanced the needle blindly, then catheter:  | Thread Did not thread |
|  Changed space  |                              |

Patient Comfort at 30 minutes (VAS  $\leq$  10/100) YES NO

Additional Number of attempts after loss of resistance 0 1 2 3 4 5

Complications (circle all that applies)

Wet tap Paresthesias Intravascular Other (please explain)

Epidural analgesia failed and then epidural Replaced? YES NO

Delivery date \_\_\_ and Time \_\_\_\_\_

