## BACKGROUND

Identification of the epidural space involves recognition of a change in pressure from one tissue plane to another. This drop of pressure, called “loss of resistance” (LOR), across a band of connective tissue into the epidural space is detected using a needle-syringe apparatus. The operator applies pressure to the plunger of the syringe until the drop in pressure is identified when the plunger collapses. The epidural catheter, a small tube that is inserted into the epidural space to give the medication, is then advanced using the needle as a guide. Confidence in locating the epidural space is based on clarity of the loss of resistance and the ease of threading the epidural catheter.

When there is difficulty in advancing the epidural catheter after the epidural space has been identified, several maneuvers are performed in order to correct the problem. These include: injecting saline through the needle to “expand” the epidural space, advancing the needle tip 1-2 mm, inserting a new flexible epidural catheter, inserting a new non-flexible epidural catheter, rotating the needle bevel, changing a patient’s posture, pulling the needle back to re-engage the *ligamentum flavum* and then performing a second LOR technique, and removing the needle entirely and performing a new placement at the same or different interspace (1). Each time a new maneuver is performed, this is considered a new attempt at threading the epidural catheter into the epidural space. Not succeeding on threading the epidural catheter correctly into the epidural space on the very first try is considered a “failure to thread,” however these maneuvers are performed until adequate labor analgesia is established in all patients. Establishing labor analgesia on the first epidural catheter threading attempt reduces the amount of time between when the epidural is requested and when pain relief is administered. A “more successful”

epidural threading attempt is related to a decrease in the time required to thread the epidural and adequately relieve labor pain.

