Once, the epidural catheter has been threaded successfully, the clinician will apply negative pressure to the catheter through a syringe in order to rule out blood or cerebro-spinal fluid (CSF) aspiration. If aspiration of blood and CSF is negative, the patient will be given our standard medications consisting of 2 ml Lidocaine 1.5% with epinephrine 1:200,000 to rule out intrathecal catheter placement. Following 2 minutes, the patients will be given additional 3 ml from the lidocaine and epinephrine mixture in order to rule out intravascular cannulation. In addition, a standard loading bolus of bupivacaine 0.125% with fentanyl 3 mcg/ml will be administered in three fractionated doses of 5 ml each, through an epidural pump. All patients will be then connected to a programmed intermittent epidural bolus pump with the following settings: bupivacaine 0.125% with fentanyl 3 mcg/ml, programmed intermittent bolus 6 ml every 45 minutes. Patient's demand bolus 6 ml every 15 minutes, without baseline infusion.

If the epidural catheter cannot be sufficiently advanced into the epidural space, one or more of the following maneuvers will be adopted: additional saline will be administered through the Tuohy needle; alternatively, a new flexible epidural catheter can be inserted; if the catheter advances following one of these afore-mentioned maneuvers, the thread will be considered successful with minor adjustments. Conversely, if the needle is rotated, re-angled, redrawn and

re-advanced or advanced blindly, these will all be considered as major needle manipulations and recorded as failure of that attempt to advance the epidural catheter. Further attempts are made until proper epidural analgesia is established.

Establishment of successful labor analgesia will be defined at a verbal analogue score equal to or less than 10 on a 100-point scale within 30 min from the standard epidural medication administration. All data related to the technical aspects of the epidural placement will be collected in the form shown in the appendix. The goal of both study groups is the management of labor pain.

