**Table 3 Success rates and complications of corrective maneuvers performed**

Maneuver	Single-orifice		Multi-orifice		Statistics
	Success (%)	Complications	Success (%)	Complications	
Saline injection	x/X (x%)	X	x/X (x%)	X	p=
Rotate needle bevel	x/X (x%)	X	x/X (x%)	X	p=
New placement	x/X (x%)	X	x/X (x%)	X	p=
Re-engage ligament, re-advance	x/X (x%)	X	x/X (x%)	X	p=
Advance needle	x/X (x%)	X	x/X (x%)	X	p=
Change needle angle	x/X (x%)	X	x/X (x%)	X	p=
New catheter	x/X (x%)	X	x/X (x%)	X	p=

Data are number (%).

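### Table 3 plans a success fraction and p-value by kit for new placements, but the study form does not directly record whether the catheter threaded after one

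*Combined protocol and SAP*

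**What the plan says.** Table 3, titled "Success rates and complications of corrective maneuvers performed", has seven rows. For each kit it provides a success fraction with a percentage and a complications entry, and each row has a cell for a p-value. One row is "New placement".

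The Background lists maneuvers used when a catheter will not advance. Among them is "removing the needle entirely and performing a new placement at the same or different interspace". Pulling the needle back to re-engage the ligament is listed there as a separate maneuver.

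The section Equipment, Technique and Study Data Collection names the data source: "All data related to the technical aspects of the epidural placement will be collected in the form shown in the appendix". It also says that attempts go on until proper analgesia is established.

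On the form, under Ease of Threading the Epidural Catheter, six maneuver boxes follow the pattern of "Changed needle angle, then catheter", each with a choice of Thread or Did not thread. The last box in the list reads only "Changed space".

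**The concern.** A success fraction needs the number of times a maneuver was tried and the number of times the catheter then threaded. For new placements the form supplies no explicit second number. It supplies the first only in part, if the row is meant to include a new placement at the same space.

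What is at stake is one planned comparison between kits. If the row is filled from the final outcome, it would show close to complete success for both kits, with a p-value, whatever happened at each new placement. If nothing is inferred, the row cannot be reported as laid out. A result that was never written down may not be recoverable afterwards.

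**Working it through.** **1. The plan's own figure, for context.** The row at issue does not enter the sample size. Inputs from Study Size: proportions 0.11 and 0.01, power 80%, level 0.05 (two-sided assumed, since sidedness is not stated).

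- Without continuity correction: n = [1.96·√(2·0.06·0.94) + 0.8416·√(0.11·0.89 + 0.01·0.99)]² / 0.10² = 87.35, so 88 per group.
- With continuity correction: n' = (87.35/4)·[1 + √(1 + 4/(87.35·0.10))]² = 106.4, so 107 per group, which is the stated figure.

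**2. Table 3 rows set against the form.**

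| Table 3 row (paraphrased) | Matching form box | Thread result on form? |
|---|---|---|
| Saline | Hydrodissection | Yes |
| Bevel rotation | Needle rotated | Yes |
| Re-engaging the ligament | Withdrawn and re-advanced with a further loss of resistance | Yes |
| Needle advanced | Advanced blindly | Yes |
| Needle angle | Angle changed | Yes |
| New catheter | New catheter, same brand | Yes |
| New placement | Changed space (different space only) | No |

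Six of the seven rows have a recorded result; one does not.

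**3. Could another field supply it?**

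- The item "Epidural analgesia failed and then epidural Replaced" concerns failed analgesia. The Background treats that as distinct from difficulty in threading, and Table 2 has its own row for replaced epidurals.
- The counter of additional attempts (0 to 5) is not tied to a maneuver, a space or a result.
- The level of placement is a single entry, so it cannot show whether a repeat used the same space.
- The box "Withdrawal and re-advanced the needle with an additional LOR" does carry a result and could absorb a same-space repeat. The repeat would then be mixed with the row for re-engaging the ligament and could not be separated from it.

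**4. What inference would do.** Suppose, hypothetically, that a patient has two new placements, the first failing to thread and the second succeeding. Counted per placement, success is 1/2. Read from the ticked box and the final successful placement, it is 1/1. The form does not record the order of maneuvers, so the two histories cannot be told apart. As every case continues until analgesia is established, the error runs towards 100% in both kits.

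**5. Scale.** At 120 placements per kit, the rates in Study Size give 0.11 × 120 = 13.2 and 0.01 × 120 = 1.2 first-attempt threading failures. These figures suggest that few cases would reach this row. They are neither an estimate of nor a limit on the number of new placements.

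**The case against.** The strongest reply is that the row matters little. Success of individual maneuvers is not among the Objectives and is not listed in Statistical Analysis; it appears only in a table shell. With perhaps one case in one kit, the comparison would say little even if perfectly recorded. This stands, and it keeps the point minor.

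Second, a reader might infer that the row cannot be computed at all. The documents do not support that. The form times the interval from loss of resistance to needle removal after successful placement. If the space was changed, every other ticked maneuver failed and a time is entered, threading after the new placement is a reasonable inference. What is lost is any intermediate failure and the order of events.

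Third, the Background list is not a definition of the Table 3 row. The authors may have meant a new placement to be a changed space only, with same-space repeats ticked under withdrawal and re-advancement. On that reading the count of cases is complete, though the result is still missing. The Background's separate listing of the two maneuvers tells against this reading, but the text does not settle it.

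Fourth, a reader might infer that one misassigned result moves the percentage by at least 1/13 = 7.7 points. That floor does not hold. The form also allows for no loss of resistance being found, which could lead to a changed space without any threading failure. The methods count threading after saline or a new catheter as success, so 13 need not be the number requiring a maneuver. Study Size does not name the kit behind the 1% either.

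A loss in reading the PDF is an unlikely explanation: the box also lacks the words about the catheter that the other six carry in their own labels.

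**Conclusion.** The point holds as a mismatch between a planned table row and the form that is meant to feed it. The result for new placements is not directly recorded, and same-space new placements have no labelled box. Partial inference is possible, but it is biased towards complete success in both kits.

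The size is small: the success column of one descriptive row in seven, with a number of cases that the documents do not allow one to derive and that is probably low. A reader might infer that scoring of the primary outcome is compromised as well. It is not, because neither that outcome nor the sample size uses this row, and complications do not depend on the missing thread result.

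The conclusion assumes that one form is completed per patient. A separate form for each new placement could supply the result, but the documents do not say that this is done.

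**What to change.** Before the study starts, replace the bare box with an item worded: New placement (same space / different space), then catheter: Thread / Did not thread. Have it completed for each new placement, so that a failed first repeat is not hidden by a later success, and state that the Table 3 row is computed from this item.

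If the form is not changed, drop the success fraction and p-value for that row and report only the count of changed spaces.

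The cost is one line on the form and one sentence defining the row. It changes recording only, with no extra procedure or staff.

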### *Study Size*

In order to determine the study size, we looked at 114 consecutive epidural placements as part of our routine quality assurance with the Arrow® Epidural Catheterization Kit at Von Voigtlander. We found that in 11% (n=12) of epidurals placed, the epidural catheter did not thread on the first attempt. In a separate quality assurance check we retrospectively reviewed 100 epidural placements finding out that in 1% (n=1) of epidurals placed, the epidural catheter did not thread on the first attempt. A sample-size analysis for the primary outcome shows that 107 epidural placements per group would provide a power of 80% to detect a difference in proportion between the two techniques of 0.10 at the 0.05 level. Considering an attrition of 10-20% for follow-up and data missing, a total number of 240 epidural placements will be collected. Power calculations were computed using PASS 14.

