**Table 2 Demographic and Epidural data collection**

Characteristics	Single-orifice N=125)	Multi-orifice N=125)	P-value
Demographics			
Age, years	XX ± X	XX ± X	X
Body Mass Index, kg/m 	XX ± X	XX ± X	X
Gestational age, weeks	XX ± X	XX ± X	X
Pain relief within 30 minutes	X (x%)	X (x%)	X
Cervical dilation (cm)	XX ± X	XX ± X	X
Catheter failure to advance	X (x%)	X (x%)	X
Dural puncture epidural	X (x%)	X (x%)	X
Accidental dural puncture	X (x%)	X (x%)	X
Paresthesia	X (x%)	X (x%)	X
Intravascular cannulation	X (x%)	X (x%)	X
Time to catheter thread	X (x%)	X (x%)	X
Number of epidural attempts	X (x%)	X (x%)	X
Epidurals replaced	X (x%)	X (x%)	X

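### The form keeps 30-minute pain only as YES/NO at 10 or less, so the 0–100 score is lost: a modest, conditional loss of sensitivity and checkability, cheap to avoid

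*Combined protocol and SAP*

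**What the plan says.** The Equipment, Technique and Study Data Collection section defines successful labor analgesia as a "verbal analogue score equal to or less than 10 on a 100-point scale within 30 min" of the standard medication. Statistical Analysis then compares the kits on "patients who have a verbal analogue pain score equal or less than 10 (scale 0 to 100) at 30 minutes following epidural medication administration"; the percentages "will be compared through the chi-square or Fisher's exact test, as appropriate, by looking at the difference in percentages of patients". Table 2 has a row "Pain relief within 30 minutes", laid out as a count and percentage.

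The study form, under Ease of Threading the Epidural Catheter, has one item for this: "Patient Comfort at 30 minutes", with the cut at 10/100 printed beside it and a YES/NO choice. There is no field for the number.

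The analgesia comparison comes last in Statistical Analysis, as an addition to the listed secondary outcomes. It does not appear among the aims in Objectives.

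**The concern.** The criterion is defined on a 101-point scale, but only one side of one cut is kept. A patient at 11 and a patient at 90 are recorded identically. The yes/no can always be derived from the score, but the score can never be recovered from the yes/no.

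Two things are at stake:

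- **Sensitivity.** If one kit shifts pain scores generally, a test on the dichotomy needs more patients than a test on the score to show it.
- **Checkability.** Type of Study describes an open-label design, and Prestudy Data Collection and Training has the provider record selected patient data. The form does not say who completes the pain item. Whoever does so can know the kit and applies the cut while filling in the form. The weekly accuracy checks in Monitoring and Quality Assurance then have no number to compare the tick with.

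**Working it through.** **1. The plan's own figure.** Study Size gives "107 epidural placements per group would provide a power of 80"%, for failure to thread of 0.11 v 0.01 at the 0.05 level. Take two-sided alpha (z = 1.960) and 80% power (z = 0.842), with mean rate 0.06:

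- n = [1.960√(2×0.06×0.94) + 0.842√(0.11×0.89 + 0.01×0.99)]² / 0.10² = (0.658 + 0.276)² / 0.01 ≈ 87.3, so 88.
- With continuity correction: (87.3/4)[1 + √(1 + 4/(87.3×0.10))]² ≈ 106.4, so 107.

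The figure reproduces, but it concerns threading. No power, effect size, SD or success rate is stated for pain, so what follows rests on assumed values.

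**2. Efficiency of the yes/no for a continuous score.** Let p be the share scoring 10 or less. Efficiency is the ratio of sample sizes (score test to yes/no test) for equal power.

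- Normal shift, against the t-test: φ(z_p)² / [p(1−p)].
- Logistic shift (proportional odds), against the rank-sum test: 3p(1−p).

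Example at p = 0.80: φ(0.842)² / 0.16 = 0.0784/0.16 = 0.49, a loss of 51%; and 3×0.16 = 0.48, a loss of 52%.

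| p (assumed) | Loss, normal | Loss, logistic |
|---|---|---|
| 0.50 | 36% | 25% |
| 0.70 | 42% | 37% |
| 0.80 | 51% | 52% |
| 0.90 | 66% | 73% |

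The loss reaches 50% only when p is about 0.79 or higher (or, by symmetry, about 0.21 or lower).

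**3. Effect of ties at 0.** With a share f of all patients at exactly 0 and proportional odds, efficiency is p(1−p) / [(1−f³)/3]. At p = 0.80 with 90% of responders at 0, f = 0.72 and efficiency is 0.16/0.209 = 0.77.

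| Responders scoring 0 | Loss at p = 0.80 | Loss at p = 0.90 |
|---|---|---|
| 50% | 49% | 70% |
| 70% | 42% | 64% |
| 90% | 23% | 42% |
| 100% | 2% | under 1% |

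**4. Simulated zero-heavy scores.** Three assumed zero-inflated gamma patterns, 120 per kit and 3,000 runs each, gave the power below for the rank test v the yes/no test. Efficiency is approximated by [(1.96 + z of yes/no power) / (1.96 + z of score power)]².

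- 44% v 25%: (1.286/1.809)² ≈ 0.505, a loss of about half.
- 67% v 59%: (2.188/2.400)² ≈ 0.83, a loss of about 17%.
- 61% v 60% (coarse scores, difference at the cut): (2.213/2.239)² ≈ 0.98, a loss of about 2%.

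These only illustrate how far the answer depends on the score pattern.

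**5. In terms of power.** For a 10-point difference in success under a normal shift, 120 per kit:

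| Success rates (assumed) | Yes/no | Score | n per kit for 80% power, yes/no v score |
|---|---|---|---|
| 0.50 v 0.40 | 34% | 50% | 388 v 245 |
| 0.80 v 0.70 | 43% | 69% | 294 v 156 |
| 0.90 v 0.80 | 58% | 93% | 199 v 82 |

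These are favorable figures. The 10–20% attrition in Study Size would leave 108 to 96 per kit, and allocation by whole weeks is ignored.

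**The case against.** The plan is consistent on this point. The definition, the analysis, the Table 2 row and the form all use a score of 10 or less, and the form supplies what the planned test needs. The cut is prespecified. Analgesia is an extra comparison in a trial sized for threading, so limited power for it is expected. The statement that pain management is the goal of both groups describes a goal of care, not a study objective. All of this stands, and it keeps the point minor.

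Some stronger readings are tempting, and the documents do not support them:

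- A reader might infer that the tick throws away half the information or more. That needs an assumed success rate near 80% or above and few ties at 0. The documents give neither; the nearest hint, in Potential Risks of Participation, is that inadequate pain control is likely.
- A reader might infer that a number is already elicited and then discarded. The definition implies a score, but no section says one is asked for and noted.
- A reader might infer that a written score would cure observer bias. It would come from the same open-label setting.

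A rank test is also not always better: if the kits differ mainly around the cut, the yes/no can do as well.

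**Conclusion.** The point holds as a low-cost improvement, not as an error. The binary test is valid, and dichotomizing does not itself bias it. What is lost is detail, some sensitivity, and the ability to verify the classification from the study data.

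For a continuous score under a general shift, the loss is about 25–36% at an assumed 50% success, about 50% at 80%, and about 66–73% at 90%. Heavy ties at 0 or coarse scoring bring it down, in some patterns to almost nothing. No single figure can be defended without the success rate and score distribution. The primary outcome is unaffected.

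**What to change.** Replace the YES/NO item with 'Pain score at 30 minutes ___ /100'. Derive the 10-or-less criterion from it at analysis, and keep the planned chi-square or Fisher comparison and the Table 2 row. Add one prespecified rank-sum comparison of the score, with median and quartiles by kit.

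Label the added test supportive. Statistical Analysis says "A p-value of 0.05 throughout will be considered statistically significant" and describes no adjustment for multiple tests, so the new test should not become a second route to a claim.

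Two wordings should be reconciled at the same time. Statistical Analysis announces unsatisfactory analgesia but counts the patients who meet the success criterion. The Methods definition allows any time up to 30 minutes, while the analysis and form refer to the 30-minute point. A stored score makes the direction unambiguous, but one 30-minute score serves only the second timing.

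The cost is writing a number instead of a tick, plus one more test on an additional comparison. Thresholds, treatment and sample size do not change. The cut becomes auditable; open-label bias remains.
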